**Permitted windows for assessments after Day 1 of Cycle 1:**

A ± 2-day time window will be allowed for Hematology, Biochemistry-A and CLcr (provided only if serum creatinine levels are above ULN) on Day 8 and Day 15, and for vital signs on Day 8 of Cycle 1.

A -1 day window will be allowed for physical examination, ECOG PS, vital signs, Hematology, Biochemistry-A, and Biochemistry-B, CLcr (provided only if serum creatinine levels are above ULN) and Pregnancy test on Day 1 of Cycle 2 and further cycles (always prior to lorbinecetin infusion).

A + 2 days window for Day 1 lorbinecetin administration of Cycle 3.

If a drug administration is delayed beyond the permitted protocol window, assessments planned for the original administration day must be repeated on the day the dose is finally administered.

a Should treatment be administered more than ten days after the screening tests, repeat these tests prior to the first infusion and if clinically indicated. Height needs to be measured at baseline only. BSA will not be reported at the EOT. BSA calculated according to DuBois formula (see [Appendix 4](#)).

b Any patient having any grade ≥ 3 laboratory abnormalities and/or treatment-related AEs is suggested to have the relevant tests re-assessed at intervals of at least 72 hours but not more than one week until recovery to at least grade 2 has been documented.

c Repeat during treatment period and at EOT if clinically indicated.

d Calculated CLcr [Cockcroft and Gault's formula] should be provided only if serum creatinine levels are above ULN.

e ECG should be done in triplicate (at screening, Day 1 and at EOT visit) and allow rhythm definition (at least 30 seconds of duration), PR interval and QT interval (raw and corrected by HR using Bazett's formula). On Day 1, 5 minutes before SOI (-25 to -1 min before preinfusion PK samples collection) and 1 hour after EOI (-15 to -1 min before the PK sample collection), both will be done in triplicate.

f A previous LVEF assessment could be used if was made within 28 days prior to screening and during treatment period and at EOT will be repeated only if clinically indicated.

g Randomization apply for study Part B only.

h Itraconazole for self-administration and the patient's diary should be given to the patient on Day -5 with a -2/+1 day time window (i.e., from Day -7 to Day -4).

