**PART B SEQUENCE 2 (RT):**

Study Period►	Screening (days prior to registration)	Cycle 1										Cycle 2										Cycle 3		End of Treatment	Follow-up AEs		
		1*	2	3	5	8	11	15	-4	-3	-2	-1	1	2	3	4	5	6	7	8	11	15	1	31 (±10)			
Written IC	(Before any study procedure)	-	-	-	-	-	-	-	-	-	-	-	-	-	-	-	-	-	-	-	-	-	-	-	-	-	
Demographic data	-14	-	-	-	-	-	-	-	-	-	-	-	-	-	-	-	-	-	-	-	-	-	-	-	-	-	
Medical history/Baseline condition	-14	-	-	-	-	-	-	-	-	-	-	-	-	-	-	-	-	-	-	-	-	-	-	-	-	-	
Primary diagnosis/Prior treatment(s)	-14	-	-	-	-	-	-	-	-	-	-	-	-	-	-	-	-	-	-	-	-	-	-	-	-	-	
Complete physical examination, including weight and BSA a	-14	X	-	-	-	-	-	-	-	-	-	-	X	-	-	-	-	-	-	-	-	-	X	X	-	-	
ECOG PS a	-14	X	-	-	-	-	-	-	-	-	-	-	X	-	-	-	-	-	-	-	-	-	X	X	-	-	
Vital signs (HR, BP, T) a	-14	X	-	-	-	X	-	-	-	-	-	-	X	-	-	-	-	-	-	X	-	-	X	-	-	-	
Hematology b	-14	X	-	-	-	X	-	X	-	-	-	-	X	-	-	-	-	-	-	X	X	X	X	X	-	-	
Coagulation (INR) c	-14	X	-	-	-	-	-	-	-	-	-	-	-	-	-	-	-	-	-	-	-	-	-	-	-	-	
Biochemistry-A b	-14	X	-	-	-	X	-	X	-	-	-	-	X	-	-	-	-	-	-	X	X	X	X	X	-	-	
Biochemistry-B b	-14	X	-	-	-	-	-	-	-	-	-	-	X	-	-	-	-	-	-	-	-	-	X	X	-	-	
Calculated CLcr (Cockcroft and Gault's formula) b, d	-14	X	-	-	-	X	-	X	-	-	-	-	X	-	-	-	-	-	-	X	-	X	X	X	-	-	
Detection of SARS-CoV-2 (COVID-19) by PCR	-14	-	-	-	-	-	-	-	-	-	-	-	-	-	-	-	-	-	-	-	-	-	-	-	-	-	
Pregnancy test (serum β-hCG) (only if the patient is a WOCBP)	-14	X	-	-	-	-	-	-	-	-	-	-	X	-	-	-	-	-	-	-	-	-	X	-	-	-	
ECG e	-14	X	-	-	-	-	-	-	-	-	-	-	X	-	-	-	-	-	-	-	-	-	-	X	-	-	
LVEF (by ECHO or MUGA) f	-14	-	-	-	-	-	-	-	-	-	-	-	-	-	-	-	-	-	-	-	-	-	-	-	-	-	
Randomization g	-14	-	-	-	-	-	-	-	-	-	-	-	-	-	-	-	-	-	-	-	-	-	-	-	-	-	
Itraconazole delivery and patient's diary h	-	-	-	-	-	-	-	-	X	-	-	-	-	-	-	-	-	-	-	-	-	-	-	-	-	-	
Prophylactic medication i	-	X	-	-	-	-	-	-	-	-	-	-	X	-	-	-	-	-	-	-	-	-	X	-	-	-	
Lurbinectedin 1h (-5/+20 min) infusion	-	X	-	-	-	-	-	-	-	-	-	-	X	-	-	-	-	-	-	-	-	-	X	-	-	-	
Itraconazole oral administration	-	-	-	-	-	-	-	-	X	X	X	X	X	X j	X	X	X	X	X	X	X	-	-	-	-	-	
Contact to patients (via telephone or other) k	-	-	-	-	-	-	-	-	X	X	X	X	-	X	X	X	X	X	X	X	-	-	-	-	-	-	
AAG blood sample collection	-	X	-	-	-	-	-	-	-	-	-	-	X	-	-	-	-	-	-	-	-	-	-	-	-	-	
IL6 blood sample collection	-	X	-	-	-	-	-	-	-	-	-	-	X	-	-	-	-	-	-	-	-	-	-	-	-	-	

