## 6.4 EVALUATIONS DURING TREATMENT

The following assessments will be done while patient is on treatment ([Table 5](#)). For a more graphic display, please refer to the table [Schedule of Assessments and Procedures](#).

**Table 5.** Evaluations during treatment.

	ASSESSMENT	TIME
1. Clinical examination	♦ Complete physical examination, including weight and calculation of BSA. a	Sequence 1 (TR) and Sequence 2 (RT): Day 1 of each cycle (always prior to lurbinectedin infusion). Also repeat on Day 1 of Cycle 1 (prior to lurbinectedin infusion) if more than ten days have passed since the screening assessment.
	♦ Vital signs: heart rate, blood pressure and body temperature.	Sequence 1 (TR) and Sequence 2 (RT): Day 1 of each cycle (always prior to lurbinectedin infusion), and Day 8 in Cycles 1 and 2. Also repeat on Day 1 of Cycle 1 (prior to lurbinectedin infusion) if more than ten days have passed since the screening assessment.
	♦ ECOG performance status ( Appendix 1 ).	Sequence 1 (TR) and Sequence 2 (RT): Day 1 of each cycle (always prior to lurbinectedin infusion).

	ASSESSMENT	TIME
		Also repeat on Day 1 of Cycle 1 (prior to lurbinecetin infusion) if more than ten days have passed since the screening assessment.
2. Laboratory testsb	
 
♦ Hematology: Differential WBC (including neutrophils, monocytes and lymphocytes), erythrocytes, hemoglobin, hematocrit and platelets.
 
♦ Biochemistry A: AST, ALT, AP, lactate dehydrogenase (LDH), creatinine, glucose, creatine phosphokinase (CPK), CPK-MB fraction (if CPK is elevated above the normal range) and gamma glutamyltransferase (GGT) and total bilirubin (direct bilirubin if total bilirubin is above the ULN).
 
♦ Biochemistry B: Serum electrolytes (Na+, K+, Mg++), total calcium, total proteins, albumin, CRP.
 
♦ Coagulation (INR):
 
♦ Calculated CLcr: Cockcroft and Gault's formula (Appendix 4).c
 
	Sequence 1 (TR) and Sequence 2 (RT): Cycle 1: Day 8 and Day 15. Also repeat on Day 1 of Cycle 1 (prior to lurbinecetin infusion) if more than ten days have passed since the screening assessment Cycle 2: Day 1, Day 8 and Day 15. Cycle 3: Day 1. (always prior to lurbinecetin infusion).

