### 6.2 *Clinical Laboratory Evaluation*

Laboratory results will be classified according to the NCI-CTCAE v.5. All laboratory visits reported as “End of treatment” visit will be mapped to the last cycle visit for each patient.

The following hematological values will be displayed: white blood cells count (WBC), neutrophil count, lymphocyte count, monocyte count, erythrocytes, hemoglobin, hematocrit and platelet count. Worst grade per patient and per cycle for anaemia, lymphopenia, neutropenia, leukopenia and thrombocytopenia during treatment will be shown.

Overall cross tabulation will be presented for the worst grade during treatment vs. the baseline toxicity grading of anaemia, lymphopenia, neutropenia, leukopenia and thrombocytopenia.

If a grade 3/4 neutropenia or thrombocytopenia increase occurs during a treatment cycle, the first day the onset value is reached (counting from the start of the cycle) will be tabulated. Time to recovery of the abnormality (i.e., grade 3/4 neutropenia or thrombocytopenia) will be assessed and defined as the time, in days, from the start of the grade 3/4 abnormality until the abnormality is recovered (grade  $\leq 2$ ). The analysis will be carried out taking into account all events, including those that occur in a same cycle. The information will be shown by means of median and range.

Likewise, the following biochemical and coagulation values will be displayed: aspartate aminotransferase (AST), alanine aminotransferase (ALT), lactate dehydrogenase (LDH), creatinine, creatinine clearance, glucose, creatine phosphokinase (CPK), CPK-MB fraction, gamma glutamyltransferase (GGT), total bilirubin, direct bilirubin, serum electrolytes (Na+, K+, Mg++, Ca++), total proteins, albumin, C-reactive protein count (CRP) and the international normalized ratio (INR). Worst grade per patient and per cycle for applicable values during treatment will be shown.

Time to recovery of the abnormality (grade 3/4 AST or ALT) will be assessed and defined as the time, in days, from the start of the grade 3/4 abnormality until recovery to grade  $\leq 2$ . The analysis will be carried out taking into account all events, including those that occur in a same cycle. The information will be shown by means of median and range.

Overall cross tabulation will be presented for the worst grade during treatment vs. the baseline toxicity grading of biochemical abnormalities.

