## 11.4.2 Biochemical Abnormalities

Table 11.4.2.1 Biochemical abnormalities: Worst grade per treatment

Part A																			
T			R																
All grades		Gr ≥ 3	Gr ≥ 4		All grades		Gr ≥ 3	Gr ≥ 4		All grades									
N(%)		N(%)	N(%)		N(%)		N(%)	N(%)		N(%)									
ALT increase																			
AST increase																			
...*																			
Part B																			
S1						S2													
T			R			R			T										
All grades		Gr ≥ 3	Gr ≥ 4	All grades		Gr ≥ 3	Gr ≥ 4	All grades		Gr ≥ 3	Gr ≥ 4								
N(%)		N(%)	N(%)	N(%)		N(%)	N(%)	N(%)		N(%)	N(%)								
ALT increase																			
AST increase																			
...*																			
Part A+B (S1)																			
T						R													
All grades		Gr ≥ 3	Gr ≥ 4	All grades		Gr ≥ 3	Gr ≥ 4	All grades		Gr ≥ 3	Gr ≥ 4								
N(%)		N(%)	N(%)	N(%)		N(%)	N(%)	N(%)		N(%)	N(%)								
ALT increase																			
AST increase																			
...*																			

Notes: Percentage is based on number of patients by study part and sequence, when applicable.

\*Creatinine increased, hyperglycemia, hypoglycemia, CPK increased, GGT increased, bilirubin increased, hypoalbuminemia, hypernatremia, hyponatremia, hyperkalemia, hypokalemia, hypermagnesemia, hypomagnesemia, hypercalcemia, hypocalcemia.

Part A, patients assigned to Sequence 1; Part B, sequence assigned randomly.

S1, Sequence 1; S2, Sequence 2.

T, Test (ITZ+LRB); R, Reference (LRB alone).

Listing 11.4.2.2 Biochemical abnormalities grade ≥ 3 by treatment

Study Part	Sequence	Treatment Group*	Subject	Event	Grade
...					

\* ITZ+LRB / LRB

Listing 11.4.2.3 Biochemical tests not assessed by treatment

Study Part	Sequence	Treatment Group*	Subject	Lab. test
...				

\* ITZ+LRB / LRB

Table 11.4.2.4 Biochemical abnormalities: Worst grade per patientpatientpatientpatientpatient

	Part A						Part B						Part A+B						Total	
	S1 (TR)			S1 (TR)			S2 (RT)			S1 (TR)			S1 (TR)			S1 (TR)				
	All grades	Gr ≥ 3	Gr ≥ 4	All grades	Gr ≥ 3	Gr ≥ 4	All grades	Gr ≥ 3	Gr ≥ 4	All grades	Gr ≥ 3	Gr ≥ 4	All grades	Gr ≥ 3	Gr ≥ 4	All grades	Gr ≥ 3	Gr ≥ 4		
	N	%	N	%	N	%	N	%	N	%	N	%	N	%	N	%	N	%		
ALT increase																				
AST increase																				
...	*																			

Notes: Percentage is based on number of patients by study part and sequence, when applicable.

Part A, patients assigned to Sequence 1; Part B, sequence assigned randomly.

S1, Sequence 1; S2, Sequence 2; TR, test-reference; RT, reference-test.

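### Protocol Table 5 puts Biochemistry B on Days 8 and 15 but the schedules do not; on the schedules, albumin and electrolyte grades are captured unequally between Test and Reference

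*Protocol*

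**What the plan says.** **Protocol Table 5 (section 6.4).** One time cell serves hematology, Biochemistry A, Biochemistry B, INR and creatinine clearance. For Cycle 1 it reads "Day 8 and Day 15. Also repeat on Day 1 of Cycle 1" (the Day 1 repeat applies if screening is more than ten days old), and for Cycle 2 "Day 1, Day 8 and Day 15". No exception is made for Biochemistry B, which is sodium, potassium and magnesium plus "total calcium, total proteins, albumin, CRP".

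**Schedules of assessments.** The Sequence 2 (RT) schedule marks Biochemistry B at screening, Day 1 of Cycles 1, 2 and 3, and EOT. Nothing is marked on Day 8 or Day 15. The Sequence 1 (TR) schedule reads the same way, subject to a caveat given in the working.

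**Window notes.** The notes under both schedules, and the one under Table 5 itself, give a ±2-day window "allowed for Hematology, Biochemistry-A and CLcr (provided only if serum creatinine levels are above ULN) on Day 8 and Day 15". Biochemistry B appears only in the one-day-early window for Day 1.

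**Protocol section 7.4.** In RT the continuation criteria are to be checked on Day 15 of Cycle 1. Albumin is one of the criteria in Table 7.

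**SAP.** Section 6.2 says: "Worst grade per patient and per cycle for applicable values during treatment will be shown". It also maps EOT laboratory visits to each patient's last cycle. Table 11.4.2.1 reports worst grade in Test and Reference columns, and its rows include "hypoalbuminemia, hypernatremia, hyponatremia, hyperkalemia, hypokalemia, hypermagnesemia, hypomagnesemia, hypercalcemia, hypocalcemia".

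**The concern.** The protocol gives sites incompatible instructions for one blood panel, and the choice decides what the SAP can report. The effect of itraconazole on the safety profile is a secondary objective, and Table 11.4.2.1 is where albumin and electrolyte abnormalities are set out by treatment. If the panel is drawn only before each Day 1 infusion and at EOT, the value showing what a cycle did is usually collected at the next cycle's Day 1 visit or at EOT. Filed by visit label, a change following one treatment can then appear under the other, or one column can lack any value taken after its own infusion.

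**Working it through.** The documents state no figure for this point, so the check sets the passages side by side and counts.

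**1. Rows affected.** Table 11.4.2.1 names ALT and AST and lists 15 more rows in its footnote: 2 + 15 = 17. Biochemistry B supplies low albumin (1) and high and low sodium, potassium, magnesium and calcium (4 × 2 = 8): 1 + 8 = 9. The other 17 − 9 = 8 come from Biochemistry A.

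**2. Draws between an infusion and the next pre-infusion visit, non-final cycle 1 or 2.**

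| Panel | Table 5 | Schedules and window notes |
|---|---|---|
| Biochemistry A | 2 (Days 8, 15) | 2 (Days 8, 15) |
| Biochemistry B | 2 (Days 8, 15) | 0 |

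**3. Where scheduled Biochemistry B values fall by visit label.** EOT goes to the last cycle, as SAP 6.2 states. Cycle 3 is counted as Reference because it is lurbinectedin alone; the SAP does not say so expressly. C1D1 means Cycle 1 Day 1, and so on; all Day 1 values are pre-infusion.

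| Sequence, last cycle | Test | Reference | Only value after an infusion of its own labelled cycle |
|---|---|---|---|
| TR, 1 | C1D1, EOT | not received | EOT, in Test |
| TR, 2 | C1D1 | C2D1, EOT | EOT, in Reference |
| TR, 3 | C1D1 | C2D1, C3D1, EOT | EOT, in Reference |
| RT, 1 | not received | C1D1, EOT | EOT, in Reference |
| RT, 2 | C2D1, EOT | C1D1 | EOT, in Test |
| RT, 3 | C2D1 | C1D1, C3D1, EOT | EOT, in Reference |

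Every patient with two or more cycles has such a value in one column and none in the other. In TR from Cycle 2 on, the column without one is always Test. The SAP's biochemistry baseline is the last value on or before the first infusion date, so the C1D1 value left in Test is also the baseline.

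**4. Patients concerned.** Part A has 3 patients, all TR. Part B has 8 randomized 1:1, so 4 TR and 4 RT. TR is 3 + 4 = 7 of 11 planned.

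**5. What precedes each C2D1 sample.** In TR, itraconazole ended on Day 8 of Cycle 1, so C2D1 follows only the Test cycle. In RT, itraconazole starts on Day -4 of Cycle 2, so C2D1 follows both lurbinectedin alone and several days of itraconazole.

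**Caveat on the TR schedule.** In the text available for this review, the second Biochemistry B mark in the TR schedule sits under Cycle 1 Day 15. The TR hematology row is displaced in the same way, with marks under Days 7 and 11 where 8 and 15 belong. I therefore read the mark as C2D1. The RT row aligns without ambiguity, and all three window notes agree with this reading.

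**The case against.** A reader might infer that the Biochemistry B rows hold no post-infusion value in any cycle. That goes too far. Both schedules and protocol section 6.5 draw the panel at EOT, 31 (±10) days after the last dose, and SAP 6.2 assigns that value to the last cycle. The gap is confined to non-final cycles.

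A reader might also infer that SAP Table 11.5.1.1 formally compares these analytes. It does not. It is planned only if applicable, and its laboratory lines are composites of any severe hematology or biochemistry abnormality, so they also draw on panels taken on Days 8 and 15 under either reading.

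Third, misfiling is not certain. SAP 7.12 leaves further conventions to a separate document, and Listing 13.24 has a calculated-cycle column, so a derivation is evidently planned. This stands as a limit: the SAP itself gives no rule for pre-infusion Day 1 samples, but one may exist elsewhere.

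Fourth, other post-infusion values may arise. The RT Day 15 check would give an albumin in the Reference cycle, and retesting is suggested after grade 3 or higher abnormalities. The first covers one analyte in one sequence and is itself absent from the schedule. The second is only a suggestion and generally needs a prior abnormal draw.

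Finally, these are descriptive rows in about 11 patients, and the protocol's main expected toxicity, myelosuppression, is sampled on Days 8 and 15 whichever text is followed. That limits the weight of the point without removing the contradiction.

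**Conclusion.** The protocol contradicts itself on Biochemistry B timing: Table 5 against both schedules and the window notes (one of them beneath Table 5), with section 7.4 also requiring a Day 15 albumin in RT that the schedule does not draw. If the schedules are followed, 9 of the 17 rows of Table 11.4.2.1 have no scheduled draw between an infusion and the next pre-infusion visit in any non-final cycle, against 2 for Biochemistry A. By visit label, capture is then unequal between Test and Reference, and TR patients who reach Cycle 2 contribute only their Cycle 1 Day 1 value to Test.

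This rests on three assumptions: sites follow the schedules and not Table 5; values are assigned by visit label, with Cycle 3 counted as Reference; and the TR row is displaced by one column in the text copy. The contradiction itself depends on none of them. The point should be corrected. It does not touch the primary pharmacokinetic comparison.

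**What to change.** 1. Reconcile Table 5, both schedules, the three window notes and section 7.4 so that one Biochemistry B timing holds, including whether albumin is drawn on Day 15 of Cycle 1 in RT.
2. If Days 8 and 15 stand, add these analytes to the Biochemistry A sample already drawn on those days. This needs no extra visit or venipuncture.
3. If the schedules stand, state in SAP 6.2 how Day 1 pre-infusion and EOT values are assigned to treatment. In TR, the Cycle 2 Day 1 value counts toward the completed Test cycle. In RT, the Cycle 2 Day 1 value is flagged and shown separately, credited to neither column: a blanket rule crediting it to the completed cycle would put an on-itraconazole value under Reference. The rule should also cover Cycle 3 Day 1 and say whether Cycle 3 counts as Reference. Table 11.4.2.1 should carry a note that Test/Reference capture of these analytes is limited.

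The cost is a protocol clarification plus either a few more analytes on existing samples, or a short SAP rule and a footnoted, less informative comparison.

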## 1. INTRODUCTION

### 1.1 INFORMATION ON THE STUDY DRUG: LURBINECTEDIN

Lurbinectedin is a novel synthetic chemical entity composed of a pentacyclic skeleton formed by two fused tetrahydroisoquinoline rings with an additional tetrahydro- $\beta$ -carboline moiety ([Figure 1](#)).

Lurbinectedin is an inhibitor of oncogenic transcription. It recognizes specific sequences in the minor groove of the DNA where it forms adducts that ultimately lead to the generation of double-strand breaks (DSBs). Additionally, it induces the specific degradation of transcribing RNA Pol II and the eviction of transcription factors from the promoters of actively transactivated genes. It is specifically active in tumors addicted to transcription. The generation of DSBs triggers an extended delay in the transition through phase S of the cell cycle with an arrest in the phases G2/M, leading to tumor cell death by apoptosis.

*In vitro*, lurbinectedin demonstrated cytotoxic effects against a broad selection of tumor types with half maximal inhibitory concentration (IC50) values in the range of 1-10 nM. Although selectivity was also seen, a clustering of sensitive tumors has not been identified. Lurbinectedin also exhibited antitumor activity against different murine models of xenografted human-derived tumor types. Lurbinectedin has been tested as a single agent or in combination with different drugs in solid tumors; while antitumor activity in hematological tumors was deemed negligible, lurbinectedin has shown activity in different solid tumors; some of the most responsive tumor types were breast, small cell lung cancer (SCLC), ovarian and endometrial cancer.

Based on current clinical data, the toxicity of lurbinectedin is predictable, reversible and manageable. The most relevant toxicity is reversible myelosuppression with a nadir occurring in the middle of the second week after Day 1 infusion in an every-three-week cycle; overall, the incidence of febrile neutropenia is below 20% in all ongoing Phase II trials.

[figure not shown]

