The most relevant toxicity found in the FiH trial was reversible myelosuppression, notably grade 4 non-febrile neutropenia in 40% of patients treated at the RD in Cycle 1. Neutropenia was generally predictable and short-lasting and rarely caused treatment delays with nadir usually occurring during the second week. No cases of febrile neutropenia occurred in this study, although patient selection might have played a role. Also, at the RD, treatment was generally well tolerated, with no grade 4 transaminase increases observed (in contrast to what occurred above the RD). No unexpected toxicities occurred in this study, and there were no signs of cumulative toxicity. All patients at this dose level were treated with standard antiemetic prophylaxis to control grade 2 nausea and/or vomiting [13].

There was one partial response as per the Response Evaluation Criteria in Solid Tumors (RECIST v. 1.0) in pancreatic cancer and three disease stabilizations (SD) at the RD lasting  $\geq 4$  months (two in soft tissue sarcomas, one in melanoma) [13].

To explore the feasibility of an alternative schedule (Day 1 and 8, q3wk), a second phase I trial (PM1183-A-005-11) was started in advanced non-colorectal cancer patients following a prospective FD escalation. The RD was 5 mg FD on Day 1 and 8 q3wk. Myelosuppression limited further dose escalation; in contrast to the FiH trial, grade 4 neutropenia lasted longer and there were more drug-related dose delays/omissions [14]. Based on the results from single-agent phase I clinical trials in solid tumors, the Day 1 q3wk schedule was assessed as more convenient with better compliance, and was selected for further clinical trials.

**Table 1.** Completed single-agent lurbinectedin phase I trials in solid tumor patients.

	PM1183-A-001-08	PM1183-A-005-11	Total
Participant sites and countries	(2): Spain, U.S.	(2): U.S.	
Schedule	1-h D1 q3wk	1-h D1, D8 q3wk	
Patients included	33	21	54
Treated patients	31	21	52
Evaluated patients	31	21	52
RD	4.0 mg/m  or 7.0 mg FD	5.0 mg FD	
Evaluable patients with DLTs at the RD (if applicable)	1 of 15: Myelosuppression	3 of 13: Myelosuppression and myelosuppression-related lack of compliance with treatment schedule	
Study status	Completed [13]	Completed [14]	

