## 7.5 DOSE REDUCTION

Patients may continue in the study treatment at a lorbinecetin reduced dose if they present any of the following:

- Grade 4 thrombocytopenia or grade 3 thrombocytopenia concomitantly with grade  $\geq 3$  bleeding.
- Two dose delays or prolonged ( $>$  one week) dose delay due to treatment-related adverse events.

- Grade  $\geq 3$  treatment related non-hematological toxicity. Exceptions are: grade  $\geq 3$  nausea and/or vomiting not optimally treated, grade 3 fatigue lasting < two days, grade 3 diarrhea lasting < one day or non-optimally treated, isolated grade 3 transient ALT/AST elevations which are rapidly reversible and not leading to subsequent delays, and non-clinically relevant isolated biochemical abnormalities.
- Grade 4 neutropenia or any grade febrile neutropenia.

Up to two dose reductions are allowed per patient. Patients who continue to experience treatment-related toxicity and/or dose delays after two dose reductions must be withdrawn from the study. Once the dose has been reduced for an individual patient, it will not be re-escalated under any circumstances.

Lurbinectedin dose reduction levels are shown in [Table 8](#).

**Table 8.** Levels of (intra-patient) lurbinectedin dose reduction in subsequent cycles in Part A and B.

Dose reduction	Lurbinectedin (q3wk) (mg/m  )	
	Lurbinectedin alone	Itraconazole co-administration cycle
1 (starting dose)	3.2	0.8
-1	2.6	0.6
-2	2.0	-

Lurbinectedin total doses in mg will be rounded to the first decimal, if necessary.  
q3wk, every three weeks.

Patients who experience any treatment-related grade 3/4 hypersensitivity and/or extravasation reactions will permanently discontinue treatment.

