#11	8	169	168 h after EOI	•	-	-	•	±24 h
#12	11	241	240 h after EOI	•	-	-	-	±24 h
#13	15	337	336 h after EOI	•	-	-	-	±48 h
#14 h	22	505	504 h after EOI	•	-	-	-	±48 h

a Additional sample for AAG and IL-6.

b Additional sample for PGt, once only, if written IC given.

c Time relative to infusion start.

d Time relative to lurbinectedin end of infusion (except PK #1).

e Sampling for itraconazole and hydroxy-itraconazole only applies in cycle with itraconazole co-administration.

f 5 min before start of infusion.

g ITZ should be administered after ITZ PK sample #1 and before the start of lurbinectedin infusion (-15 min to -1 min).

h Only in Sequence 2 (RT), and if detectable lurbinectedin concentrations are present at preinfusion sample in Cycle 2 of Part A. It should be collected before the lurbinectedin infusion starts at Day 1 of Cycle 3 if any.

AAG, alpha 1-acid glycoprotein; EOI, end of infusion; fu, unbound fraction; h, hour; IC, informed consent; IL-6, Interleukin 6; EOI, end of infusion; ITZ, itraconazole; min, minute; PGt, pharmacogenetic; PK, pharmacokinetic; RT, reference-test; SOI, start of infusion.

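### Table 5's routine blood counts skip Days 11–12, where the protocol places the nadir, and the Sequence 2 schedule grid disagrees with Table 5 about a Day 11 count

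*Protocol*

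**What the plan says.** Protocol Section 1.1 describes the main toxicity as "reversible myelosuppression with a nadir occurring in the middle of the second week after Day 1 infusion in an every-three-week cycle". Section 1.1.3.1 adds, for the first-in-human study: "Neutropenia was generally predictable and short-lasting and rarely caused treatment delays with nadir usually occurring during the second week".

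The laboratory row of Table 5 (Section 6.4) applies to both sequences. For Cycle 1 it lists "Day 8 and Day 15. Also repeat on Day 1 of Cycle 1 (prior to lurbinecetin infusion", the Day 1 repeat applying when screening is more than ten days old. For Cycle 2 it lists Days 1, 8 and 15. The permitted-windows note says that a ± "2-day time window will be allowed for Hematology, Biochemistry-A and CLcr" on Days 8 and 15. Table 5 has no Day 11 count, although Table 9 (Section 8.1.1) schedules PK sample #12 on Day 11, "240 h after EOI", with a ±24-hour window, in both cycles.

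The Part B Sequence 2 grid differs. As extracted, its Hematology row marks Cycle 1 on Days 1, 8 and 15, and Cycle 2 on Days 1, 8, 11 and 15. Biochemistry-A shows the same pattern. The creatinine clearance row has no Day 11 mark.

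These counts feed several outputs and decisions. SAP Section 6.2 states: "Worst grade per patient and per cycle for anaemia, lymphopenia, neutropenia, leukopenia and thrombocytopenia during treatment will be shown". SAP Table 11.4.3.2 reports the days of onset, nadir and recovery for neutrophils and platelets. SAP Section 11.5 compares grade 4 and grade 3/4 events between the combination and lurbinectedin alone, laboratory abnormalities included. Protocol Section 7.5 lists "Grade 4 neutropenia or any grade febrile neutropenia" among the dose-reduction criteria.

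**The concern.** The routine counts sit on either side of the period in which the protocol expects the lowest values. A patient at grade 1–2 on Day 8 who falls to grade 4 and recovers before the Day 15 visit leaves no laboratory trace. SAP Section 11.2 itself says that laboratory events such as neutropenia may be under-reported as adverse events and are better judged from laboratory results, so the scheduled counts are the main measure of the main toxicity.

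The numbers are small enough for single misses to count. Part A has three patients, and its safety results inform the Part B dose; one missed grade 4 value there is one patient in three. In Part B one patient is 1/8 = 12.5%.

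The conflict between the grid and Table 5 is a separate problem. If sites follow the Sequence 2 grid there and Table 5 elsewhere, one Test cycle gets a near-nadir count that its own Reference cycle lacks. That raises the chance of recording grade 3/4 under Test and biases the safety comparison.

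**Working it through.** The plan states no detection rate and no grade 4 duration, so there is no figure to reproduce. The check has four parts.

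**1. Coverage of the windows.** The Schedule defines Day 8 as seven days after infusion and Day 15 as fourteen, each ±2 days.
- Day 8 visit: 8 − 2 to 8 + 2 = Days 6–10.
- Day 15 visit: 15 − 2 to 15 + 2 = Days 13–17.
- Uncovered: Days 11 and 12.
- Gap between counts: 15 − 8 = 7 days nominally; 13 − 10 = 3 at least; 17 − 6 = 11 at most.

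The middle of the second week is (8 + 15)/2 = Day 11.5. With counts on the nominal days and a nadir at 11.5, the nearest count is 3.5 days away, and every episode centred there and shorter than 7 days is missed.

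**2. Share missed, nadir fixed at Day 11.5.** Assume that visits fall evenly over the five days of each window and that the grade 4 episode is centred on the nadir. The share missed is the product of the two visits' miss probabilities.
- 3 days (Day 10 to 13): each window has 1 of 5 days inside; (4/5) × (4/5) = 0.64.
- 5 days (Day 9 to 14): 2 of 5 each; (3/5) × (3/5) = 0.36.
- 7 days (Day 8 to 15): 3 of 5 each; (2/5) × (2/5) = 0.16.

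**3. Share missed, nadir varying.** Simulation of 400,000 episodes per setting, nadir Normal with mean 11.5 and the SD shown, before any retest unless stated:

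| Setting | 3-day | 5-day | 7-day |
|---|---|---|---|
| Exact Days 8 and 15, SD 1 to 2 | 70–95% | 39–68% | 0% |
| ±2-day windows, SD 1 to 2 | 62–73% | 35–45% | 14–21% |
| ±2-day windows, SD 1.5 | 66% | 39% | 17% |
| Same, plus Day 11 ±1 | 23% | 4% | 0% |
| Exact days, SD 1.5 | 82% | 50% | 0% |
| Same, plus 72-hour retest if Day 8 is grade ≥3 | 66, 41 or 16% | 25, 0 or 0% | 0% |

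The three retest values assume that grade ≥3 lasts 2, 4 or 6 days longer than grade 4. With exact days and SD 1.5, the mean distance from the true nadir to the nearest count is 2.3 days, or 0.9 days with a Day 11 count.

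**4. Reading the grids.** The Sequence 2 Hematology row has one entry per column, so its Day 11 mark in Cycle 2 can be placed. The Sequence 1 row is misaligned in the extracted text. It carries nine marks after screening, whereas Table 5 plus Day 1 of Cycle 1 and the end-of-treatment visit account for eight (Cycle 1 Days 1, 8, 15; Cycle 2 Days 1, 8, 15; Cycle 3 Day 1; end of treatment). The ninth cannot be placed.

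**The case against.** **Retests.** Table 5 footnote b and Section 8.3 provide for repeat tests after a grade ≥3 finding, and the table above shows that these recover many episodes. This stands in part. The rule helps only a patient already at grade ≥3 on Day 8. Footnote b words it as a suggestion, Section 8.3 as something that should be done. In Sequence 1 the interval runs from 72 hours to one week, so the next count may be Day 15. SAP Section 6.1 instead says at least every 72 hours.

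**Other signals.** Dose reduction also depends on febrile neutropenia, thrombocytopenia, delays and non-hematological toxicity; adverse events are collected throughout; Day 1 recovery criteria apply. SAP Table 11.4.3.2 gives way to a listing if few patients reach grade ≥3, the SAP 11.5 model is conditional, and the primary objective is PK. All true. This limits the consequence but does not supply the missing count.

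**Equal gap.** Under Table 5 the count days are the same for Test and Reference, so the shared gap does not by itself make ascertainment unequal. This stands. The unequal-ascertainment concern rests on the Sequence 2 grid mark.

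**A stronger reading.** A reader might infer that grade 4 neutropenia will often be missed, that no cycle has a Day 11 count, or that adding Day 11 would catch every episode. The documents support none of these. They give no duration, and the short-lasting description comes from a study whose recommended dose was 4.0 mg/m², not from this trial's doses. One grid does mark Day 11, and the Sequence 1 grid cannot be read. A 3-day episode on Days 11–13 would still escape a Day 11 ±1 count with probability 1/3 and the Day 15 window with probability 4/5: 1/3 × 4/5 = 27% missed, 73% caught.

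**Conclusion.** Two things are established from the text. Table 5's routine counts skip Days 11–12, where the protocol places the nadir, so from those counts the nadir and onset days can only be visit days. And Table 5 and the Sequence 2 grid contradict each other on a Day 11 count in a Test cycle.

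How many episodes would be missed is not established. The 62–73% (3-day) and 14–21% (7-day) figures are shares of grade 4 episodes, not of patients. They depend on assumed durations, a nadir varying around Day 11.5 with SD 1 to 2 days, visits spread evenly over ±2 days, and no retest. Whether the grids make Test and Reference counts unequal overall depends on the Sequence 1 grid, which must be checked in the original document. The point affects the safety objective and the reading of Part A, not the primary PK analysis. It is worth correcting because blood is already drawn on Day 11.

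**What to change.** 1. Reconcile Table 5 with both schedule grids, checking the Sequence 1 grid against the original, so that Test and Reference cycles in both sequences have the same hematology days. Settle the Biochemistry-A mark on Day 11 at the same time.
2. As a measurement change only, collect hematology at the existing Day 11 PK #12 draw in Cycles 1 and 2 of both sequences.
3. If Day 11 is not added, state in the SAP that onset and nadir days are limited to visit days, and report them so.
4. Reconcile the retest wording in Table 5 footnote b, Section 8.3 and SAP Section 6.1.

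The cost is amendment wording and one tube per cycle: 11 patients × 2 cycles = about 22 tubes, with no new visit (two more for each replacement patient). The downside should be stated openly: more grade 4 values may be recorded, and these may trigger existing rules. No dose or treatment rule is proposed here.
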